Although achievement of an SVR has been associated with laboratory and histological improvements in chronic HCV, the SVR endpoint is a surrogate for the ultimate aim of therapy, which is prevention of progression to cirrhosis, end-stage liver disease, hepatocellular carcinoma, and death from liver disease. These "hard" clinical endpoints, however, generally take years to decades to occur, making them impractical and unethical primary endpoints for clinical trials of HCV therapies. Thus the relationship between SVR to clinical outcomes must be evaluated through long-term follow-up studies.

In contrast to what is known from studies from IFN-based regimens, little data is available to date for SVR and long-term clinical outcomes for subjects who have been treated with DAA plus IFN and RBV, or IFN and RBV-free all DAA regimens. Such studies are needed in order to demonstrate the long-term benefits of DAAs, whether given with IFN and/or RBV, or given as all-DAA regimens.

AbbVie is currently developing 2 "next generation" DAA drugs for use together or in combination with a third DAA or Ribavirin. AbbVie's next generation DAAs, including ABT-493, an NS3/4A protease inhibitor and ABT-530, an NS5A inhibitor are denoted

"next generation" compounds because each demonstrated potent antiviral activity against all major HCV GTs in vitro with no or little loss of potency against known common single resistance mutants.

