### **5.2.1 Inclusion Criteria**

A subject will be eligible for study participation if he or she meets the following criteria:

1. The subject is male or female 18 years of age or older.
2. The subject has received at least one dose of an ABT-493- and/or ABT-530 containing regimen in a prior AbbVie HCV Phase 2 or 3 study (see Appendix D for list of eligible prior studies).
3. The interval between the last dose of the AbbVie DAA therapy from the previous clinical study and enrollment in Study M13-576 must be no longer than 2 years for subjects who have not been retreated. Subjects who have been treated with a commercially-available anti-HCV treatment may be enrolled greater than 2 years after the last dose of the AbbVie DAA therapy from the previous clinical study.
4. The subject must voluntarily sign and date the informed consent form approved by an Independent Review Board or Ethics Committee prior to the initiation of any study-specific procedures.
5. Subject completed the post-treatment period of an eligible prior study.

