### **8.1.3 Safety**

Serious adverse events will be coded using the Medical Dictionary for Regulatory Activities (MedDRA) and tabulated by system organ class (SOC) and preferred term (PT). A summary of medical events related to the progression of liver disease and shifts in laboratory measurements will be provided.

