6.0 Analysis Conventions

6.1 Definition of Baseline and Final Assessment

Definition of Baseline and Final Treatment Visit Value (Previous Study)

[figure not shown]
Baseline is defined as the last non-missing measurement before the first dose of study drug **in the previous study**. The final treatment visit value is defined as the last non-missing measurement collected after baseline and within 2 days of the last dose of study drug **in the previous study**.

Definition of Day 1 and Study Days (Study M13-576)

Day 1 refers to the Day 1 visit in Study M13-576. Study days in Study M13-576 are calculated for each time point relative to the Day 1 visit in this study. Study days are negative values when the time point of interest is prior to Day 1. Study days are positive values when the time point of interest is after Day 1. There is no Study Day 0. Study Days will be used to summarize hematology, clinical chemistry, and additional laboratory tests (IP-10, INR, and serum albumin) collected within this study.

Definition of Study Drug End Days (Days Relative to the Last Dose of Study Drug in the Previous Study)

Study drug end days are calculated relative to the last dose of study drug **in the previous study**. The last day of study drug is defined as Study Drug End Day 0. Days before it has negative study drug end days and days after it have positive study drug end days. Study

drug end days will be used to define the SVR windows from the previous study, and HCV RNA and resistance endpoints within this study.

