11.2 Analysis of Medical Events Related to Liver Disease or HCV Infection

Any events related to liver disease progression and/or HCV infection that are considered to be clinically significant by the investigator and begin or worsen after Day 1 will be captured on the appropriate Medical Events eCRF(s). These significant events include but are not limited to: the development of cirrhosis, events indicative of hepatic decompensation, changes in Child-Pugh classification, liver transplantation, hepatocellular carcinoma, and/or death.

The number and percentage of subjects who reported each and any of the following medical events will be summarized:

ABT-493/ABT-530
M13-576 – Statistical Analysis Plan
Version 1.0 – 23 Aug 2019

- development of cirrhosis,
- hepatic decompensation variceal bleeding,
- hepatic decompensation new ascites,
- hepatic decompensation spontaneous bacterial peritonitis,
- hepatic decompensation hepatic encephalopathy,
- hepatic decompensation hepato-renal syndrome,
- hepatic decompensation hepatic hydrothorax,
- other evidence of hepatic decompensation,
- change in the Child-Pugh category,
- hepatocellular carcinoma,
- occurrence of liver transplantation,
- death.
- other.

Listings of each medical event will be provided. In addition, listings of any liver diagnostic testing that is collected (e.g., liver biopsy or FibroScan scores) will be provided.

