11.3 Analysis of Laboratory Data

Data collected from the central and local laboratories, including additional laboratory testing due to an SAE, will be used in all analyses.

Hematology variables include: platelet count

Chemistry variables include: total bilirubin, alpha-fetoprotein, gamma glutamyl transferase (GGT), alpha2-macroglobulin, AST, ALT, haptoglobin, and apolipoprotein A1.

Additional variables include: FibroTest, IP-10, INR, and serum albumin.

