11.3.1 Statistical Methods

Each protocol-specified laboratory parameter will be summarized at each applicable study visit (e.g., Day 1, Month 3, Month 6, etc. as defined in the protocol) with the sample size, visit mean, SD, minimum, median, and maximum.

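### The SAP's liver-progression outputs fall short of the protocol: lab shifts are dropped without record, APRI has no planned output, and two event percentages use denominators that include subjects not at risk

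*SAP*

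**What the plan says.** **Laboratory data.** The protocol (8.1.3, repeated in the synopsis) says that a summary of liver events and "shifts in laboratory measurements will be provided". SAP 11.3.1 plans, for each parameter and visit, only "sample size, visit mean, SD, minimum, median, and maximum". SAP 12.0 lists three departures from the protocol: listings only for resistance, IL28B removed, and a wider population for reinfection. The loss of the shifts is not among them.

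**Time axis.** SAP 6.1 and Table 2 place laboratory data on days since the M13-576 Day 1 visit: "Study Days will be used to summarize hematology, clinical chemistry, and additional laboratory tests (IP-10, INR, and serum albumin) collected within this study". Virology uses days since last dose: "drug end days will be used to define the SVR windows from the previous study, and HCV RNA and resistance endpoints within this study". For subjects not retreated, the gap from last dose to enrolment "must be no longer than 2 years for subjects who have not been retreated" (Protocol 5.2.1). Protocol Appendix C, Table A, note b ends participation at the visit nearest to 3 years after last dose.

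**APRI.** It is a secondary measure in Protocol 4.0 and SAP 4.1, and the synopsis pairs it with FibroTest as a measure of progression. SAP 11.3 lists platelets and AST, and then "Additional variables include: FibroTest, IP-10, INR, and serum albumin". APRI is in none of its lists.

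**Events.** SAP 11.2: "The number and percentage of subjects who reported each and any of the following medical events will be summarized". The rows include development of cirrhosis and change in Child-Pugh category. No denominator is stated, so the full-analysis-set default of SAP 5.1 and 11.0 applies. Listings of every event are also planned.

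**The concern.** Progression is change within a subject. A table of visit means without change or shift shows it only if the same subjects stand behind each mean, and here they do not. A drift in bilirubin or FibroTest across visits could be a change in who was measured. The protocol's shift summary would have guarded against this, and a reader of the SAP's change log would not learn that it is gone.

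Without a line and a derivation for APRI, a named secondary measure may go unreported or be derived ad hoc at programming.

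For Child-Pugh change and new cirrhosis, a percentage that counts subjects who cannot have the event understates how often it occurs in those who can. The table alone gives no way to recover the right figure.

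**Working it through.** The study has no sample size, power or alpha calculation, so there is none to reproduce. The visit windows can be reproduced.

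**1. SAP Table 2.** Nominal day = 30 × month + 1 gives 91, 181, 361, 541, 721, 901 and 1081. Midpoints between neighbouring visits are 136, 271, 451, 631, 811 and 991. Both sets match Table 2.

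**2. Who can reach each visit.** Inputs: 30-day months (SAP Table 2), a stop at the visit nearest 3 × 365.25 = 1095.75 days after last dose (Appendix C, note b), and a maximum gap of about 730 days (Protocol 5.2.1). A subject with entry gap g is g + 30m days past last dose at Month m. The later visit of a neighbouring pair is nearer to the stop when g < 1095.75 − 30 × (mean of the two months).

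| Visit reached | Cut-off for g | Largest g (days) | Months (÷ 30.5, as in SAP 8.0) |
|---|---|---|---|
| Month 18 | 1095.75 − 30 × 15 = 645.75 | 645 | 21.1 |
| Month 24 | 1095.75 − 30 × 21 = 465.75 | 465 | 15.2 |
| Month 30 | 1095.75 − 30 × 27 = 285.75 | 285 | 9.3 |
| Month 36 | 1095.75 − 30 × 33 = 105.75 | 105 | 3.4 |

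The latest entrant is at 730 + 360 = 1090 days at Month 12, so everyone not lost or retreated can contribute up to Month 12. Selection by entry date starts at Month 18. The minimum gap is the length of the prior study's post-treatment period, which the documents do not give. If it is 12 weeks (84 days), only entrants at days 84 to 105 reach Month 36; if it is 24 weeks (168 days), nobody does.

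**3. What is measured when (Appendix C, Table A).** IP-10, platelets and the chemistry behind FibroTest and APRI are drawn at Day 1, Months 3, 6 and 24, Month 30 if it is the final visit, and Month 36. For these, the step from Month 6 to Month 24 loses everyone who entered after about day 465. At Months 12 and 18 the only chemistry is total bilirubin, in cirrhotic subjects only (note f). Its mean therefore moves from all subjects at Month 6, to cirrhotic subjects at Months 12 and 18, to all earlier entrants at Month 24.

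**4. Denominators.** Appendix E scores Child-Pugh only in cirrhotic subjects, and new cirrhosis needs a subject without it. Printed percentage = share at risk × percentage among those at risk. The documents give no cirrhotic share or event rate for this cohort, so the inputs are assumptions.

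| Assumed cirrhotic share | Child-Pugh change, 10% of cirrhotics | New cirrhosis, 2% of non-cirrhotics |
|---|---|---|
| 10% | 1.0% | 1.8% |
| 20% | 2.0% | 1.6% |
| 30% | 3.0% | 1.4% |
| 40% | 4.0% | 1.2% |

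Child-Pugh change is understated 10-fold to 2.5-fold. New cirrhosis is affected much less.

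**The case against.** The strongest reply is that the secondary objectives are only to summarise and that Protocol 5.6.1 calls the analyses purely descriptive. Counts, percentages and full event listings meet that literally. This stands: a reader might infer that the outputs cannot answer the secondary objective, and the documents do not support that. It does not excuse the shifts, which the protocol itself specified.

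The time axis is also defensible. Table 2 follows the protocol's visit schedule. With a 12-week minimum gap, Month 6 does pool 264 to 910 days (weeks 38 to 130) after treatment. But moving sparsely drawn tests into 12-week windows from last dose would leave most windows thin and the early ones filled only by early entrants, so the composition problem would move rather than go away.

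On APRI, SAP 11.3.1 speaks of every laboratory parameter the protocol specifies, which may be meant to include it, and its components are listed. That makes the gap a clarification, but a derivation is still missing.

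The pooled denominator is inferred from the full-analysis-set default, not stated. That is fair, and it is a reason to state one.

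Two further readings go too far. The Introduction says the "relationship between SVR to clinical outcomes must be evaluated through long-term follow-up studies", which may suggest that pooling SVR12 achievers with failures breaks a commitment. That sentence is background; no split by SVR status and no person-time rate is promised, and SAP 12.0 notes that failures are few. Nor is it established that events between the prior study and Day 1 go uncounted: Protocol 5.3.1.1 records them on the Medical Events form at Day 1, the summary sentence in SAP 11.2 carries no date limit, and SAP 7.2 tabulates medical history.

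**Conclusion.** The point holds as a should-fix conformity and interpretation gap with three parts.

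- **Shifts.** Promised in two places in the protocol, absent from SAP 11.3.1 and not logged in SAP 12.0. This needs no assumption. The resulting visit means are not comparable from Month 12 on for total bilirubin and from Month 24 on for the fibrosis-related tests. The entry limits of about 15 months (Month 24) and 9 months (Month 30) follow from the documents' own rules at nominal visit days.
- **APRI.** Missing from the analysis variable lists and without a derivation. This needs no assumption either.
- **Denominators.** Child-Pugh change and new cirrhosis default to the whole full analysis set. The direction of the error is certain if that default is applied. The 1% to 4% range is only an illustration and rests on the assumed cirrhotic shares and the assumed 10% rate.

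None of this touches the primary durability or resistance analyses.

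**What to change.** **SAP 11.3.** Add APRI with its derivation from AST and platelets. Add within-subject change and category shifts from M13-576 Day 1, and from the previous-study baseline where a value exists, for FibroTest, APRI, IP-10, AST, platelets and the Child-Pugh laboratory tests (bilirubin, albumin, INR). State the categories, since neither document gives any for FibroTest or APRI. Present total bilirubin by cirrhosis status. If the sponsor prefers not to produce shifts, record the deletion and the reason in SAP 12.0.

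**SAP 11.2.** State the denominators: subjects without cirrhosis at Day 1 for new cirrhosis; and, for Child-Pugh change, subjects with cirrhosis at entry or developed during the study who have at least two Child-Pugh assessments. The two-assessment condition matters because scoring began only after Amendment 2 was approved at each site (Appendix C, note d). Any reported change in a subject outside that set should be footnoted and remains in the listing.

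**Optional.** A supportive laboratory display by time since last DAA dose in wide windows, and events by SVR12 status.

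**Cost.** SAP wording and programming. The study measurements are already collected, and SAP 7.1 already carries prior-study cirrhosis status, which the Day 1 history can update. The downside is a few more tables, some with small cells.

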6.2 Definition of Analysis Windows

For efficacy analyses of HCV RNA and resistance, the time windows specified in Table 1 describe how efficacy data are assigned to analysis (or SVR) windows during the Post-Treatment Period of the previous study and in Study M13-576. All time points and corresponding time windows are defined based on the blood sample collection date.

For safety laboratory data collected within Study M13-576, the time windows specified in **Table 2** describe how data are assigned to protocol-specified time points.

If more than one assessment is included in a time window, the assessment closest (except in analyses of SVR) to the nominal time will be used. If there are two observations equally distant to the nominal time, the latest one will be used in analyses. For analyses of SVR, the last value in the window will be used.

If multiple measurements are made on the same day, the average of the values will be used to calculate descriptive statistics, except baseline values (see Section 6.1).

Table 1. Analysis Time Windows for HCV RNA and Resistance Endpoints

[figure not shown]
Scheduled Visit	Nominal Day (Study Drug End Day)	Time Window (Study Drug End Days Range)
Post-Treatment Week 4 (SVR ₄)	28	3 to 56
Post-Treatment Week 12 (SVR ₁₂)	84	57 to 126
Post-Treatment Week 24 (SVR ₂₄)	168	127 to 210
Post-Treatment Week 36	252	211 to 294
Post-Treatment Week 48	336	295 to 378
Post-Treatment Week 60	420	379 to 462
Post-Treatment Week 72	504	463 to 546
Post-Treatment Week 84	588	547 to 630
Post-Treatment Week 96	672	631 to 714
Post-Treatment Week 108	756	715 to 798
Post-Treatment Week 120	840	799 to 882
Post-Treatment Week 132	924	883 to 966
Post-Treatment Week 144	1008	967 to 1050
Post-Treatment Week 156	1092	1051 to 9,999

Note: The result closest to the scheduled time point will be used, except for SVR endpoints, where the last HCV RNA value in the window will be used.

Table 2. Analysis Time Windows for Study M13-576 Protocol Defined Assessments, other than HCV RNA and Resistance

Scheduled Visit	Nominal Day (Study Day)	Time Window (Study Days Range)
Day 1	1	1
Month 3	91	2 to 136
Month 6	181	137 to 271
Month 12	361	272 to 451
Month 18	541	452 to 631
Month 24	721	632 to 811
Month 30	901	812 to 991
Month 36	1081	992 to 9,999

Note: A month is defined as 30 days. The closest value in the window will be used.

6.3 Missing Data Imputation

The values of SVR₄, SVR₁₂, and SVR₂₄ will be derived from the previous study as needed

For subjects in the full analysis set, if a subject starts another treatment for HCV, then all HCV RNA values for this subject measured on or after the start date of the new HCV treatment will be excluded from the analyses of SVR and virologic failure. The subject will be considered a failure for summaries of viral response at all time points after the start of the new HCV treatment.

Missing Data Imputation for Virologic Failure

If HCV RNA values from the central laboratory are missing but a local laboratory value is present in the appropriate time period, then the local laboratory value will be used to assess post-treatment relapse.

6.4 Overall Type-I Error Control

There is no hypothesis testing for the efficacy analyses, therefore no multiplicity adjustment will be performed for the study.

7.0 Demographics, Baseline Characteristics, Medical History, and Previous/Concomitant Medications

Demographics, baseline characteristics, medical history, and previous/concomitant medications will be summarized on the full analysis set, unless otherwise specified.

7.1 Demographic and Baseline Characteristics

Demographics as captured on the eCRF in Study M13-576 will be summarized. Other demographics (e.g., baseline BMI) and baseline characteristics as captured in the previous study will be summarized.

Demographics will include:

- Age (continuous; < 65 or ≥ 65 years; < 75 or ≥ 75 years), per Study M13-576 database;
- Sex, per Study M13-576 eCRF;
- Ethnicity, per Study M13-576 eCRF;
- Race, per Study M13-576 eCRF;
- Baseline BMI (continuous; $< 30 \text{ or } \ge 30 \text{ kg/m}^2$), per previous study;
- Country, per Study M13-576 database;
- Region (Europe, North America, or rest of world), per Study M13-576 database;
- Previous study number, per Study M13-576 eCRF;
- Previous assigned treatment duration (8, 12, or 16 weeks), per previous study.

Baseline characteristics will include:

- HCV genotype (1, 2, 3, 4, 5, and 6) and subtype (1a, 1b, 2a, 3a, etc.), per previous study;
- IL28B genotype (CC, CT, or TT; CC or non-CC), per previous study;
- Treatment status prior to previous study (naïve or experienced [PRS, NS5A naïve/PI experienced, NS5A experienced/PI naïve, NS5A experienced/PI experienced]), per previous study;
- Baseline log_{10} HCV RNA levels (continuous) and (< 1,000,000, \geq 1,000,000 to < 2,000,000, \geq 2,000,000 IU/mL), per previous study;
- Baseline cirrhosis status in prior study, per Study M13-576 eCRF;
- Baseline HIV-1/HCV coinfection status, per previous study;
- Tobacco and alcohol use; as captured on the Study M13-576 eCRF;
- Baseline injection drug use status, per previous study;
- Baseline status on use of stable opiate substitution, per previous study;
- Concomitant use of proton pump inhibitors (PPIs) during prior study.

Summary statistics (N, mean, median, standard deviation (SD), and range) will be generated for continuous variables (e.g., age and BMI) and the number and percentage of subjects will be presented for categorical variables (e.g., sex and race).

7.2 Medical History

[figure not shown]
Medical history data will be summarized and presented using body systems and conditions/diagnoses, as recorded in the Study M13-576 medical history dataset. The body systems will be presented in alphabetical order and the conditions/diagnoses will be presented in alphabetical order within each body system. The number and percentage of subjects with a particular condition/diagnosis will be summarized. Subjects reporting more than one condition/diagnosis within a body system will be counted only once for that body system.

7.3 Previous Treatment and Concomitant Medications

The number and percentage of subjects taking prior HCV medications (prior to entry in the previous study) or concomitant medications as captured on the eCRFs in Study M13-576 will be summarized by generic drug name based on the WHO Drug Dictionary.

The study drug regimen (e.g., ABT-493 300 mg QD + ABT-530 120 mg QD or ABT-493/ABT-530 300 mg/120 mg) and treatment duration (e.g., 8, 12, or 16 weeks; if the assigned treatment duration was extended, then the final assigned treatment duration will be counted) assigned in the previous studies will be summarized for each regimen and duration combination. The regimens will be summarized, with the respective final assigned duration (8, 12, or 16 weeks), as:

- ABT-450/r + ABT-530 + RBV
- ABT-493 200 mg QD + ABT-530 40 mg QD
- ABT-493 200 mg QD + ABT-530 80 mg QD
- ABT-493 200 mg QD + ABT-530 120 mg QD
- ABT-493 200 mg QD + ABT-530 120 mg QD + RBV
- ABT-493 300 mg QD + ABT-530 120 mg QD
- ABT-493 300 mg QD + ABT-530 120 mg QD + RBV
- ABT-493/ABT-530 300 mg/120 mg QD

Medications related to the treatment of HCV will be collected in the PT Period (including previous study and Study M13-576) and will be summarized by generic drug name separately for subjects in the full analysis set and for subjects excluded from the full analysis set. A post-treatment medication for the treatment of HCV is defined as any medication taken on or after the last dose of study drug in the previous study and entered as "Post treatment HCV medications" on the eCRF in Study M13-576 or similarly on the eCRF in the prior study.

8.0 Subject Disposition

The number of subjects for each of the following categories will be summarized overall and by investigator, based on all enrolled subjects.

- Enrolled subjects;
- Subjects who completed the study;
- Subjects who discontinued from the study;
- Subjects who are in the full analysis set.

The number and percentage of subjects in the full analysis set who discontinued from the study will be summarized by reason (all reasons) and by primary reason as recorded on the eCRF.

The duration of follow-up will be summarized both in days and in months for the full analysis set. Duration of follow-up in days is defined for each subject as the last HCV RNA measurement date in Study M13-576 minus the last study drug dose date (in the previous study) plus 1 day. Duration of follow-up in months will be calculated as duration days/30.5. Descriptive statistics (mean, SD, median, minimum, and maximum) will be presented for each measure of duration of follow-up.

A listing of subjects who are excluded from the full analysis set will be provided.

